7.2.1.2 Acute lung injury score

Rules for derivation of Acute lung injury score are reported in section 11.1.

Value and change from baseline in Acute lung injury score will be analyzed at Day 2, Day 3, Day 7, Day 14 (if still intubated) timepoints by means of descriptive statistics as a continuous variable. Comparison between treatments will be performed by means of two-sample t-test and, if assumption of normality is not confirmed, two-sample Mann-Whitney U test.

Acute lung injury score classes (as defined in section 11.1.1.) will also be summarized as a categorical variable: number and percentage of patients in each class for each timepoint will be presented and a shift table will be provided.

7.2.1.3 SOFA scores

Up to CRF V6.0, sites entered in eCRF the single items and the SOFA score was automatically calculated. Starting from CRF V7.0 sites have either

1) the possibility to complete the single items (if they are all available) and get the SOFA Score automatically calculated

OR

2) they can enter the total SOFA score manually, without completing the single items.

Summaries will not differentiate between these two methods of collecting the total SOFA score (i.e. will report the total score regardless if it is manually entered or automatically calculated from single items).

Standard/Forms/Template				
Title		Statistical Analysis Plan Template		
Code		Version	Effective Date	Page
PPD		01	29 Aug 2022	49 of 78

If both scores (manually and automatically calculated) are present, the value automatically calculated will be used in the analysis.

Value and change from baseline in SOFA score will be analyzed at Day 2, Day 3, Day 7, Day 14 (if still intubated) timepoints by means of descriptive statistics as a continuous variable. Comparison between treatments will be performed by means of two-sample t-test and, if assumptions of normality is not confirmed, two-sample Mann-Whitney U test.

7.2.1.4 Ventilatory ratio

Rules for derivation of Ventilatory ratio are reported in section 11.1.

Value and change from baseline in Ventilatory ratio will be analyzed at Day 2, Day 3, Day 7, Day 14 (if still intubated) timepoints by means of descriptive statistics as a continuous variable. Comparison between treatments will be performed by means of two-sample t-test and, if assumptions of normality is not confirmed, two-sample Mann-Whitney U test.

7.2.1.5 Incidence of ECMO

Rules for derivation of Incidence of ECMO are reported in section 11.1.

The number and proportion of patients requiring ECMO will be reported at Day 14 and compared by means of Fisher's exact test or Chi-squared test, depending on data distribution.

7.2.1.6 Use of vasoactive medications

Vasoactive medication use will be defined as described in Section 11.1.

The proportion of patients with at least one vasoactive medication by Day 14 (as defined in section 11.1.1) will be compared by Fisher's exact test or Chi-squared test, depending on data distribution.

7.2.1.7 CXR assessment of pulmonary edema by “radiographic assessment of lung edema” (RALE) score

Value and change from baseline in RALE score will be analyzed at Day 2, Day 3, Day 7, Day 14 (if still intubated) timepoints by means of descriptive statistics as a continuous variable. Comparison between treatments will be performed by means of two-sample t-test and, if assumptions of normality is not confirmed, two-sample Mann-Whitney U test.

7.2.1.8 Percentage of patients achieving pressure support ventilation equal to 5 cmH₂O with PEEP equal to 5 cmH₂O for 2 hours (measure of weaning) by day 28 and at hospital discharge

The proportion of patients achieving pressure support ventilation equal to 5 cmH₂O with PEEP equal to 5 cmH₂O for 2 hours (measure of weaning) by Day 28 and at hospital discharge will be compared by Fisher's exact test or Chi-square's test, depending on data distribution.

7.2.1.9 ICU-free days at Day 28 and at Hospital Discharge

Rules for derivation of ICU-free days are reported in section 11.1.

ICU-free days will be analyzed by means of descriptive statistics as a continuous variable at Day 28 and at hospital discharge. Comparison between treatments will be performed by means of two-sample t-test and, if assumptions of normality is not confirmed, two-sample Mann-Whitney U test.

Standard/Forms/Template				
Title		Statistical Analysis Plan Template		
Code		Version	Effective Date	Page
PPD		01	29 Aug 2022	50 of 78

7.2.1.10 Hospital-free days at Day 28

Rules for derivation of hospital-free days are reported in section 11.1.

The hospital-free days by Day 28 will be analyzed by means of descriptive statistics as a continuous variable. Comparison between treatments will be performed by means of two-sample t-test and, if assumptions of normality is not confirmed, two-sample Mann-Whitney U test.

7.2.1.11 Incidence of tracheostomies

Rules for derivation of Incidence of tracheostomies are reported in section 11.1.

The proportion of patients with tracheostomies by Day 28 and at hospital discharge will be compared by Fisher's exact test or Chi-square's test, depending on data distribution.

7.2.1.12 Incidence of transfer to long term acute care (LTAC) facility

Rules for derivation of Incidence of transfer to LTAC facility are reported in section 11.1.

The proportion of patients with transfer to LTAC facility by Day 28 and at hospital discharge will be compared by Fisher's exact test or Chi-square's test, depending on data distribution.

7.2.1.13 All-cause mortality by day 28 and by day 60

Rules for derivation of All-cause mortality by day 28 and by day 60 are reported in section 11.1.

The number and proportion of deaths within Day 28 and within Day 60 will be reported and compared by Fisher's exact test.

Freedom from death will also be analyzed and graphically represented as described in Section 4.1 following a time-to-event approach.

An additional analysis for time to death will be performed where study discontinuations for Adverse Event, Death, and Loss to follow-up will be considered as failure events.

7.2.1.14 Patients discharged by day 28

The number and proportion of patients discharged (alive) at Day 28 (as defined in section 11.1) will be reported and compared by Fisher's exact test.

7.2.1.15 Change from baseline to Day 3, 7 and 14 in plasma levels of IL-6, IL-8, PAI-1, Plasma TNFr-1, ICAM-1, RAGE

Value and change from baseline to Day 3, 7 and 14 in biomarkers plasma levels of IL-6, IL-8, PAI-1, Plasma TNFr-1, ICAM-1, RAGE will be analyzed by means of descriptive statistics as a continuous variable. Comparison between treatments will be performed by means of two-sample t-test and, if assumptions of normality is not confirmed, two-sample Mann-Whitney U test.

Boxplot for values and changes from baseline will also be graphically represented by treatment at each timepoint.

In the case parameters are reported with a result containing a qualifier (e.g.: "<2.5", ">3.4") the value will be analyzed by stripping out the qualifiers:

- if the value contains a qualifier "<" with a decimal place (<X.X), the value will be analyzed as: X.X;

Standard/Forms/Template				
Title		Statistical Analysis Plan Template		
Code		Version	Effective Date	Page
PPD		01	29 Aug 2022	51 of 78

- if the value contains a qualifier “>” with a decimal place (>X.X) the value will be analyzed as: X.X.

A listing on biomarkers results will be provided as well.

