3.3 Sample size justification

The sample size of the study is calculated based on results from literature [5-8]. Evaluation of the efficacy for this study is being accomplished through estimation of a 95% confidence interval. No hypotheses are specified for this study and no p-values are being calculated but for descriptive purposes, therefore no level of significance is specified.

Considering a randomization ratio 1:1 (reparixin vs. placebo), a sample size of 60 evaluable subjects is considered adequate for assessing the difference between groups in primary endpoints, i.e., change from baseline in OI at day 7 and VFD at day 28.

The given sample size will provide a reasonable precision in the estimation of group differences in primary endpoints to an expected margin of error for a 95% one-sided confidence interval of at most 46.5% the standard deviation, whatever it is:

Standard/Forms/Template				
Title		Statistical Analysis Plan Template		
Code		Version	Effective Date	Page
PPD		01	29 Aug 2022	20 of 78

- Assuming a standard deviation of 11.5 points for OI, the 95% one-sided confidence interval for the difference between groups will have a width of 5.35 points;
- Assuming a standard deviation of 8 days for VFD, the 95% one-sided confidence interval for the difference between groups will have a width of 3.75 days.

If 10% of enrolled patients will not be evaluable for primary analysis, the total number of patients to be enrolled will be approximately 66.

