7.2 Analysis of secondary efficacy endpoints

7.2.1 Analysis details

Independently of results on primary, all secondary endpoints (Section 0) will be analyzed and compared by treatment by means of descriptive statistics and by appropriate parametric tests depending on the nature of the variable and its distribution. No multiplicity correction is required. Statistical tests for continuous variables will be performed only for the change from baseline.

The assumption of normality requested by parametric statistical tests, will be checked as described in section 4.1, and in case such assumptions are not met, also non-parametric counterpart tests will be performed. Change from baseline value (for continuous variables) and shift tables versus baseline (for categorical variables) may also be summarized for all post-baseline visits, as described in the following sections. Alpha level to be used for secondary endpoints is 0.05 two-sided.

7.2.1.1 Change in OI from baseline to Day 4

Value and change in OI from baseline to Day 4 will be analyzed by means of descriptive statistics as a continuous variable. Comparison between treatments will be performed by means of two-sample t-test and, if assumptions of normality is not confirmed, two-sample Mann-Whitney U test.

Change from baseline to Day 4 is derived similarly to change from baseline to day 7: details on derivation are provided in section 11.1.1.

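### For the secondary endpoints, mortality included, the SAP text names a between-arm test but no between-arm effect estimate with a confidence interval, although the plan says efficacy is judged by estimation

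*SAP*

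**What the plan says.** SAP 3.3, repeating Protocol 9.1, sets the framework: "Evaluation of the efficacy for this study is being accomplished through estimation of a 95% confidence interval". It adds: "No hypotheses are specified for this study and no p-values are being calculated but for descriptive purposes". The precision statement that follows is tied to the primary endpoints: "a sample size of 60 evaluable subjects is considered adequate for assessing the difference between groups in primary endpoints".

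The primary analyses keep to this. Protocol 9.5.1.1 and SAP 7.1.1.1 and 7.1.1.2 plan an adjusted treatment difference with a two-sided 90% interval for the change in oxygenation index (OI) at Day 7 and for ventilator-free days (VFD) at Day 28. The one-sided p-value is shown for description.

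For the secondary endpoints, SAP 7.2.1 says they are "compared by treatment by means of descriptive statistics and by appropriate parametric tests", at a two-sided alpha of 0.05. The subsections then name the comparison:

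- continuous endpoints: t-test, with Mann-Whitney if normality is not confirmed;
- binary endpoints: Fisher or chi-squared;
- mortality: "The number and proportion of deaths within Day 28 and within Day 60 will be reported and compared by" Fisher's exact test, plus Kaplan-Meier curves with the log-rank test (SAP 4.1).

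The intervals in SAP 4.1 and Protocol 9.5 are by arm: around a mean, around a proportion (Wilson, with continuity correction in the SAP) or around each Kaplan-Meier curve (Greenwood).

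**The concern.** A proof-of-concept trial of about 66 patients is run to learn which effects remain plausible, so that the next study can be sized. Mortality, ICU-free days, organ-failure scores and biomarkers all bear on that decision. A p-value does not say how large an effect the data allow in either direction. Two per-arm intervals do not replace an interval for the difference, because they can overlap widely whatever the difference supports. If the comparison is specified only as a test, the reader gets less than the estimation framework leads them to expect, for all 16 secondary endpoints in SAP 3.5.2. The choice of effect measure and interval is also left open until after unblinding.

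**Working it through.** **1. The plan's own precision figure.** Inputs from SAP 3.3: 60 evaluable, 1:1, so 30 per arm; one-sided 95% interval; stated margin at most 46.5% of the SD.

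- Margin/SD = t(0.95, 58 df) x sqrt(2/30) = 1.672 x 0.2582 = 43.2% (42.5% with the normal quantile).
- Multiplying by sqrt(chi-squared(0.80, 58)/58), which allows 80% assurance on the observed SD, gives 46.3%. At 29 per arm it is 47.2%, so 30 per arm is the smallest size that meets 46.5%. The plan does not state the 80% assurance; it is an assumption here. The plain formulas also satisfy the stated bound.
- 0.465 x 11.5 = 5.35 points for OI, as stated. 0.465 x 8 = 3.72 days for VFD, against 3.75 stated.

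The figure reproduces, but it covers the primary endpoints only. The plan gives no between-arm precision for any secondary endpoint.

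**2. What is planned and what can be derived from it.**

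| Endpoint type | Planned per arm | Planned between arms | Derivable by the reader |
|---|---|---|---|
| Binary | count, %, Wilson interval where applicable | Fisher or chi-squared | crude risk difference and interval |
| Continuous, t-test | n, mean, SD, quartiles, interval where applicable | t-test | mean difference and interval |
| Continuous, Mann-Whitney | same | Mann-Whitney | no Hodges-Lehmann shift |
| Time to death | Kaplan-Meier curve, Greenwood limits | log-rank | no direct hazard ratio |

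**3. Mortality example.** The counts are assumed: 8/33 versus 13/33, with 33 = 66/2.

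- p1 = 8/33 = 24.2%; p2 = 13/33 = 39.4%; difference d = -15.2 points. Two-sided Fisher p = 0.290.
- Wilson 95% limits without correction: 12.8% to 41.0%, and 24.7% to 56.3%. They overlap widely.
- Newcombe lower limit = d - sqrt((p1 - l1)^2 + (u2 - p2)^2) = -0.152 - sqrt(0.114^2 + 0.169^2) = -0.356.
- Newcombe upper limit = d + sqrt((u1 - p1)^2 + (p2 - l2)^2) = -0.152 + sqrt(0.168^2 + 0.147^2) = +0.072.
- With the continuity-corrected Wilson limits (11.7% to 42.6%, and 23.4% to 57.8%) the same formula gives -0.374 to +0.092.

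**4. Expected precision for mortality.** The range of 27% to 45% is in Protocol 2.6.2.3. With a common rate p and n per arm, the 95% half-width is 1.96 x sqrt(2p(1 - p)/n). At n = 33 it is 21 points for p = 27% and 24 points for p = 45%. At n = 30 it is 22 and 25 points.

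**5. What the test can show.** Exact power of two-sided Fisher at 33 per arm if mortality were halved is 18%, 27% and 40% for control mortality of 27%, 36% (midpoint) and 45%. This does not extend to every large effect. A t-test at 33 per arm has 89% power for 0.8 SD, and Fisher has 86% power for 10% versus 45%.

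**The case against.** The strongest reply has four parts.

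First, the trial does give between-arm effect sizes. Both primary endpoints have adjusted differences with intervals, and VFD scores death as 0, so mortality enters one of them. This stands. A reader might infer from SAP 7.2.1 that the trial yields no between-arm effect size for planning; the documents do not support that.

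Second, the tests do not stand alone. Counts, proportions, means and SDs by arm are planned, and crude risk and mean differences follow from them. This also stands, but it leaves the contrast and its method to the reader, and it does not supply a Hodges-Lehmann shift or a hazard ratio.

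Third, Protocol 9.5.1.2 openly plans descriptive statistics and tests for the secondary endpoints, so SAP 7.2.1 breaks no explicit promise. That is fair. The estimation sentence speaks of efficacy in general, but the precision target names only the primary endpoints. The point is a mismatch with the stated framework, not a breach of a specific commitment.

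Fourth, the table shells are in an appendix that is not among the documents, so a difference column may exist there. That cannot be excluded. The SAP text still does not require one.

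It is also tempting to say that nearly every secondary p-value will be non-significant even when the effect is large. The power figures in step 5 contradict that as a general statement.

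**Conclusion.** The point holds in limited form. For the secondary endpoints the SAP text names only a test as the between-arm comparison and specifies no effect estimate with an interval, while the same plan states an estimation framework and applies it to the primary endpoints. The consequence is clearest for mortality. The interval for the risk difference would reach roughly 21 to 25 points either side, and a Fisher p-value does not show this. That size rests on 30 to 33 patients per arm and the mortality range quoted in the protocol; the 8/33 versus 13/33 example rests on assumed counts. Endpoints measured only in patients still intubated will have fewer patients and wider intervals. The primary analysis is unaffected. This is a cheap reporting improvement, worth making before unblinding.

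**What to change.** In SAP 7.2.1, make the between-arm estimate with a two-sided 95% confidence interval the stated comparison:

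- **Binary endpoints:** risk difference with a Newcombe interval, stating whether it is continuity-corrected. SAP 4.1 uses the corrected Wilson interval per arm, so the corrected form would match it.
- **Continuous endpoints:** mean difference with its interval, and the Hodges-Lehmann shift with its interval wherever Mann-Whitney is used.
- **Death:** Kaplan-Meier difference at Day 28 and Day 60 with Greenwood standard errors, or a hazard ratio.

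Keep the p-values as the descriptive extra that SAP 3.3 says they are. If the table shells already carry these differences, the change is to the SAP text only. Otherwise it costs one column per secondary table. The downside is more unadjusted intervals to read, which a sentence noting that they are not corrected for multiplicity would cover. No new data or patients are needed.

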7.3 Analysis of exploratory efficacy endpoints

Not applicable.

8. Evaluation of Safety

8.1 Adverse events

Adverse Events (AEs) started before administration of study treatment will be considered as pre-treatment; any AE started on or after the date of the administration of the first dose of study medication or started prior to the administration of the first dose and worsened in severity after the administration of the first dose will be considered as TEAE.

In case of missing or incomplete dates not allowing a direct allocation to any of the two categories of AEs (pre-treatment/TEAE), an allocation will be done according to the available parts of the onset and the end dates (Table 4 in section 11.1.2). In case of TEAE, the event can be further classified as:

1. On Treatment period, or
2. On Follow-up period

according to the available parts of the onset and the end dates (Table 4).

All AEs will be coded by SOC and PT according to MedDRA Version 25.0 (or later) thesaurus.

In addition, each AE will be graded to capture the relationship to IMP and severity. “Possible”, “Probable” and “Highly Probable” or missing relationships will be considered as related to study drug (ADR – Adverse Drug Reaction) for the summary tables. “None” and “Unlikely” relationships will be considered not related to study drug.

Pre-treatment AEs will be presented in the listings only.

TEAE summaries will be presented, displaying frequencies and percentages of patients reporting TEAEs within each SOC in decreasing order of total frequency. Along with TAEs, number of events will be reported. On each of these summaries, patients will be counted only once per SOC and, within each SOC, patients will be counted only once per PT.

The following tables and listings will be presented by treatment group:

- An overview of TEAEs including:
 - the number of patients who exhibited at least one TEAE, at least one severe TEAE, at least one serious TEAE, at least one non-serious TEAE, at least one ADR, at least one serious ADR, at least one TEAE leading to discontinuation of IMP, at least one TEAE

Standard/Forms/Template				
Title		Statistical Analysis Plan Template		
Code		Version	Effective Date	Page
PPD		01	29 Aug 2022	52 of 78

leading to discontinuation of study, at least one TEAE leading to death, at least one secondary infection TEAE by Day 28 and by hospital discharge,

- the number of TEAEs, number of non-serious TEAEs, number of TESAEs, number of ADRs, number of serious ADRs, number of severe TEAEs, number of TEAEs leading to discontinuation of IMP, number of TEAEs leading to discontinuation of study, number of TEAEs leading to deaths, number of secondary infection TEAEs by Day 28 and by hospital discharge.
- Summary of TEAEs by primary SOC and PT and by study period (on treatment/follow-up and overall).
- Summary of TEAEs by primary SOC, PT and Severity.
- Summary of Serious TEAEs by Primary SOC and PT and by study period (on treatment/follow-up and overall).
- Summary of Treatment Emergent ADRs by Primary SOC and PT and by study period (on treatment/follow-up and overall).
- Summary of Treatment Emergent ADRs by Primary SOC and PT and Severity.
- Summary of TEAEs leading to IMP Discontinuation by Primary SOC and PT and by study period (on treatment/follow-up and overall).
- Summary of TEAEs leading to study Discontinuation by Primary SOC and PT and by study period (on treatment/follow-up and overall).
- Summary of TEAEs leading to Death by Primary SOC and PT.
- Summary of secondary infection TEAEs by Day 28 and by hospital discharge by Primary SOC and PT.
- Listing of all pre-treatment AEs.
- Listing of all TEAEs.
- Listing of serious TEAE.
- Listing of Treatment Emergent ADR.
- Listing of Serious Treatment Emergent ADR.
- Listing of all TEAEs leading to IMP discontinuation.
- Listing of all TEAEs leading to study discontinuation.
- Listing of all TEAEs leading to death.
- Listing of Deaths.
- A summary of Deaths will also be provided as table reporting mean time to death (time to death as derived as date of death-randomization date+1), Autopsy performed, number of deaths (overall and by day), and the proximate cause of death (overall and by day)
- Listing of secondary infections (as defined in Section 11.1).

8.2 Clinical laboratory evaluation

Analysis of clinical laboratories data will be performed by treatment for Hematology and Biochemistry (including eGFR) tests. In case of different units of measure considered for the same laboratory

Standard/Forms/Template				
Title		Statistical Analysis Plan Template		
Code		Version	Effective Date	Page
PPD		01	29 Aug 2022	53 of 78

parameter, all values will be converted into Standard International units (if applicable) or to the same unit. Even if laboratory are collected at screening and the protocol mention changes from screening, baseline and changes from baseline will be provided: this means that, if for some reason the screening assessment is done after treatment start date (by mistake or any reason), the value will not be considered in the analysis, since the value will not be flagged as "Baseline" (as defined in section 3.2.2). Subsequent timepoints are Day 3, Day 7, Day 14, Day 21, end of treatment, Day 28 and hospital discharge.

The following summaries will be provided:

- A summary table showing for all laboratory tests the values and changes from baseline to each subsequent visit.
- A summary table showing for all laboratory tests the frequency of the investigator's interpretation at each available visit.
- Shift tables presenting the number and the percentage of patients in each bivariate category (baseline versus each post-baseline visit) with regards to investigator's interpretation.

The following graphical representations will be provided for all laboratory parameters:

- Spaghetti plot of individuals' observed data and change from baseline (with x-axis marked by days relative to start of actual treatment);
- Boxplot for values and changes from baseline by actual treatment at each timepoint.

Listings showing hematology results, biochemistry results, abnormal clinically significant hematology results and abnormal clinically significant biochemistry results will be provided.

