5.3.2. Criteria for permanent discontinuation of the IMP

The IMP must be discontinued in the case:

- Upon initiation of renal replacement therapy;
- Upon increase of ALT and/or AST to ≥ 3 x ULN and total bilirubin > 2 x ULN or upon increase of ALT and/or AST to ≥ 5 x ULN
- The patient is discharged home;
- Withdrawal of informed consent by the patient or his/her legal representative (in this case, the patient / representative will be asked whether they consent to usage of the data already collected in the study; if not, the data will be deleted);
- Pregnancy occurs;
- Development of Serious AE probably or possibly related to IMP, as per PI's judgment;
- Inadvertent missing of 3 or more consecutive doses of the IMP;
- Inability to resolve within 24 hours any medical condition/event that led to temporary withholding of the IMP (see also 5.3.3.);
- Recurrence of AE probably or possibly related to IMP upon re-introduction of the IMP.

Occurrence of renal or hepatic dysfunction will be monitored as part of the biochemistry data set through safety laboratory tests obtained at day 3 ± 8 h, 7 ± 1 , 14 ± 2 , and 21 (if the IMP is meant to be administered up to 21 days). The other criteria that qualify the patient to treatment discontinuation will be monitored daily.

If the IMP administration is prematurely discontinued, the primary reason for discontinuation must be recorded in the eCRF. Patients who discontinue the treatment with the IMP will NOT be withdrawn from the study by default and will be asked to complete safety and efficacy observations as per the protocol unless they withdraw their consent.

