Renal function will be evaluated by estimated Glomerular Filtration Rate (eGFR), calculated using the 2021 Chronic Kidney Disease Epidemiology Collaboration (2021 CKD-EPI) as per the following formula:

$$\text{eGFR}_{\text{cr}} = 142 \times \min(S_{\text{cr}}/\kappa, 1)^{\alpha} \times \max(S_{\text{cr}}/\kappa, 1)^{-1.200} \times 0.9938^{\text{Age}} \times 1.012 \quad [\text{if female}]$$

where:

S_{cr} = standardized serum creatinine in mg/dL

κ = 0.7 (females) or 0.9 (males)

α = -0.241 (female) or -0.302 (male)

$\min(S_{\text{cr}}/\kappa, 1)$ is the minimum of S_{cr}/κ or 1.0

$\max(S_{\text{cr}}/\kappa, 1)$ is the maximum of S_{cr}/κ or 1.0

Age (years)

From: [CKD-EPI Creatinine Equation \(2021\) | National Kidney Foundation](#)

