3.6 Safety endpoints

- Haematology/biochemistry tests change from screening to day 3±8h, 7±1, 14±2, 21±2 (if still receiving reparixin), 28±2 visits and at hospital discharge [by visit]
- eGFR, absolute value and change from screening to day 3±8h, 7±1, 14±2, 21±2 (if still receiving reparixin), 28±2 visits and hospital discharge [by visit]
- Hepatic Function (ALT/AST, total/direct bilirubin), absolute values and change from screening to day 3±8h, 7±1, 14±2, 21±2 (if still receiving reparixin) visits and at hospital discharge [by visit]

Standard/Forms/Template				
Title		Statistical Analysis Plan Template		
Code		Version	Effective Date	Page
PPD		01	29 Aug 2022	23 of 78

- ECG/rhythm analysis changes from screening to day 3 ± 8 h, 7 ± 1 , 14 ± 2 , 21 ± 2 (if still receiving reparixin), 28 ± 2 visits and hospital discharge. [by visit]
- Incidence of secondary infections defined as new (occurring after the first IMP intake) infection in a previously known to be sterile site, including blood, body fluid or tissue, or new pathogen isolated from cultures of biological samples known to be previously infected by day 28 [study day: see section 11.1.1]
- Incidence of TEAEs and TESAEs from the beginning of study treatment to up to the end of study participation.
- Vital Signs change from baseline to daily assessment through extubation (namely, day 1, day 2, day 3, day 7, day 14, day 21) [study day: date/time]

4. Statistical Analysis

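### SAP 8.2 has no rule for creatinine and eGFR measured on renal replacement therapy, so these values can mask renal failure in the laboratory summaries

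*SAP*

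**What the plan says.** SAP 8.2 states: "Analysis of clinical laboratories data will be performed by treatment for Hematology and Biochemistry (including eGFR) tests". The planned output is "A summary table showing for all laboratory tests the values and changes from baseline to each subsequent visit", plus boxplots and individual-patient plots. The schedule runs past the end of treatment: "Subsequent timepoints are Day 3, Day 7, Day 14, Day 21, end of treatment, Day 28 and hospital discharge". eGFR is a safety endpoint in its own right in SAP 3.6: "eGFR, absolute value and change from screening to day 3±8h", and on to later visits.

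Under SAP 4.10, continuous summaries use whatever values are non-missing, and any exception is to be declared. None is declared for renal replacement therapy (RRT). The readable text of the SAP, including the derivation table in 11.1.1, does not mention RRT or dialysis.

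The protocol does expect RRT. Section 5.3.2 lists among the reasons for permanently stopping study drug: "Upon initiation of renal replacement therapy". It adds: "Patients who discontinue the treatment with the IMP will NOT be withdrawn from the study by default". These patients are asked to complete the remaining safety observations. Protocol 14.4.9 gives the 2021 CKD-EPI formula for eGFR, in which serum creatinine is the only laboratory input.

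**The concern.** RRT clears creatinine. A creatinine-based formula applied to a patient on RRT therefore does not describe that patient's own kidneys. It returns a higher eGFR than native function would support. Under the plan as written, such values enter the means, changes, boxplots and individual plots on the same footing as values from patients without RRT.

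The distortion falls on the patients who matter most for renal safety. Starting RRT is the only renal criterion for stopping study drug in Protocol 5.3.2, and the same section relies on the scheduled biochemistry to monitor renal dysfunction. The arm with more RRT gets more of the upward push, so a true difference in a named safety endpoint is made smaller.

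A second feature concerns change from baseline. Exclusion criterion 2 (Protocol 4.2) admits a patient whose chronic renal function is unknown unless acute RRT is already in use or imminent. Creatinine can therefore be raised at entry, and a value on RRT can then lie below it.

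**Working it through.** The plan states no figure on this point, so there is none to reproduce. The check applies the protocol's own formula to assumed creatinine values.

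**Formula** (Protocol 14.4.9), for a man aged 60 with creatinine Scr above 0.9 mg/dL: eGFR = 142 × (Scr/0.9)^(-1.200) × 0.9938^60.

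| Creatinine (mg/dL) | eGFR (mL/min/1.73m²) |
|---|---|
| 1.0 | 86.2 |
| 1.5 | 53.0 |
| 2.0 | 37.5 |
| 2.5 | 28.7 |
| 3.0 | 23.1 |
| 5.0 | 12.5 |

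**One patient, value at a visit.** Assume creatinine 5.0 before RRT (eGFR 12.5).
- At 2.5 on RRT: 28.7 - 12.5 = +16.2, with no renal recovery.
- At 1.5 on RRT: 53.0 - 12.5 = +40.5, with no renal recovery.

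**One patient, change from baseline.**
- Entry 1.0, on RRT 1.5: 53.0 - 86.2 = -33.2. This is still a decline, against 12.5 - 86.2 = -73.7 before RRT.
- Entry 2.0, on RRT 2.5: 28.7 - 37.5 = -8.8, still a decline.
- Entry 2.0, on RRT 1.5: 53.0 - 37.5 = +15.5, an apparent improvement.
- Entry 3.0, on RRT 2.0: 37.5 - 23.1 = +14.4, an apparent improvement.

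**Mean of one arm.** With 30 evaluable patients per arm (60 in total, 1:1), the upward shift relative to creatinine 5.0 is (number on RRT) × (16.2 to 40.5) / 30:
- 3 on RRT: 1.6 to 4.0
- 6 on RRT: 3.2 to 8.1
- 9 on RRT: 4.9 to 12.1

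**Difference between arms.** Assume RRT in 20% of one arm and 10% of the other, eGFR 75 without RRT in both, and a true value of 12 with RRT.
- True: (0.8×75 + 0.2×12) - (0.9×75 + 0.1×12) = 62.4 - 68.7 = -6.3.
- On-RRT value reads 29: 0.1 × (29 - 75) = -4.6. Lost: 1 - 4.6/6.3 = 27%.
- On-RRT value reads 53: 0.1 × (53 - 75) = -2.2. Lost: 1 - 2.2/6.3 = 65%.

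**Simple exclusion of on-RRT patients.** On the same inputs the means become 75 against 75. The difference is 0, and all of the -6.3 is lost.

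**The case against.** The strongest reply is that renal failure has other routes into the report.
- Protocol 8.2 requires clinically relevant untoward changes to be reported as adverse events whatever their cause. SAP 8.1 tabulates these by seriousness, severity, period and whether they led to stopping study drug.
- SAP 5.3 tabulates reasons for stopping study drug, and SAP 11.1.1 shows that the CRF records which discontinuation criterion applied.
- SAP 8.2 itself tabulates investigator interpretation, with shift tables and listings of clinically significant results.
- The table shells sit in an appendix that is not part of the documents, and the trial is a descriptive study of about 66 patients with no hypotheses.

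Most of this stands, and it limits the point to the numeric laboratory summaries and plots. It does not close the gap. RRT started after study drug has ended cannot be a reason for stopping it. SAP 5.3 does not say that the specific criterion will be tabulated. Adverse event tables by system organ class and preferred term do not group RRT, and the interpretation shift tables have no on-RRT category.

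Three stronger readings are tempting but not supported.
- A reader might infer that kidney failure is recorded as recovery throughout the report. The routes above show otherwise.
- A reader might infer that the arm difference changes sign. In the illustration it shrinks but stays negative; reversal would need an on-RRT eGFR above 75.
- A reader might infer that the SOFA renal item fails in the same way. Protocol 14.4.2 scores creatinine or urine output and takes the worst value in 24 hours, so low urine output on RRT still scores 3 or 4.

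**Conclusion.** The omission is real. Followed as written, the plan treats creatinine and eGFR on RRT as native kidney function in a named safety endpoint. The values can mask renal failure in the laboratory summaries and plots. They appear as improvement from baseline mainly when entry creatinine was already raised.

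The direction follows from the formula once RRT lowers creatinine. The size is an illustration: the RRT rates, the creatinine on RRT, the eGFR without RRT and the native value are all assumptions, and sample timing relative to RRT is unknown. Under those stated, 27% to 65% of the arm difference is lost.

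No primary result or formal safety decision rests on mean eGFR. This is a worthwhile and inexpensive correction to the safety analysis, not a defect that undermines the trial.

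**What to change.** In SAP 8.2 and 11.1.1:
- Derive an on-RRT flag with a start date and, where applicable, a stop date. Take it from the discontinuation criterion and the adverse event and procedure records, with a data query for RRT started after the last dose of study drug. The stop date matters: without it, a patient who comes off RRT could never show true recovery at Day 28 or discharge.
- State that creatinine and eGFR obtained while on RRT are not treated as native function, in tables or plots.
- Keep every patient in a categorical eGFR summary by visit, with on-RRT as the worst category.
- Give off-RRT means with their n only alongside that summary, never alone, because exclusion by itself can erase the difference.
- Add a table of RRT started by Day 28 by arm in the safety set, including RRT started after study drug ended.

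The cost is one derived flag, one added table, the categorical summary and possibly some data queries. Nothing in patient management changes.
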